6.3 Lifestyle Restrictions

6.3.1 Meals and Dietary Restrictions for CDK 4/6 Inhibitor

- Participants must avoid consumption of grapefruit, grapefruit hybrids, pummelos, star-fruit, Seville oranges, pomegranates, or products containing the juice of each during the entire study treatment and preferably 7 days before the first dose of study medications, as they affect CYP and P-glycoprotein (PgP) activity and have a potential to increase exposure to palbociclib (NOTE: Oranges and orange juice are allowed.)
- Herbal or dietary supplements known as strong inhibitors or inducers of CYP3A4 (refer to [Appendix 10](#) [Concomitant Medications]) are prohibited.

6.4 Screen Failures

Screen failures are defined as participants who consent to participate in the clinical study but who are not subsequently randomized in the study/included in the analysis population. A minimal set of screen failure information is required to ensure transparent reporting of screen failure participants, to meet the Consolidated Standards of Reporting Trials (CONSORT) publishing requirements, as applicable, and to respond to queries from regulatory authorities. Minimal information includes date of consent, demography, screen failure details, eligibility criteria, and any serious AEs.

6.4.1 Retesting During Screening or Lead-In Phase

Participant Re-enrollment: This study permits the re-enrollment of a participant that has discontinued the study as a pretreatment failure (ie, participant has not been randomized/has not been treated). If re-enrolled, the participant must be re-consented.

Retesting of laboratory parameters and/or other assessments within any single Screening or Safety Run-in Phase will be permitted (in addition to any parameters that require a confirmatory value).

The most current result prior to randomization is the value by which study inclusion will be assessed, as it represents the participant's most current, clinical state.

7 TREATMENT

Study treatment is defined as any investigational treatment(s), marketed product(s), placebo, or medical device intended to be administered to a study participant according to the study randomization or treatment allocation.

Study treatment includes both Investigational [Medicinal] Product (IP/IMP) and Non-investigational [Medicinal] Product (Non-IP/Non-IMP) and can consist of the following:

- BMS-936558 (nivolumab)
- Abemaciclib
- Palbociclib
- Anastrozole

An IP, also known as an IMP in some regions, is defined a pharmaceutical form of an active substance or placebo being tested or used as a reference in a clinical study, including products already with a marketing authorization but used or assembled (formulated or packaged) differently than the authorized form, or used for an unauthorized indication, or when used to gain further information about the authorized form.

Description and storage information for the 4 drugs used in this open-label study are provided in [Table 7-1](#).

Other medications used as support or escape medication for preventative, diagnostic, or therapeutic reasons, as components of the SOC for a given diagnosis, may be considered as non-IPs.

Premedications or medications used to treat infusion-related reactions should be sourced by the investigative sites if available and permitted by local regulations.

Table 7-1: Study Treatments for Study Number CA2097A8

Product Description/ Class and Dosage Form	Potency	IP/Non-IMP	Blinded or Open Label	Packaging/ Appearance	Storage Conditions (per label)
Nivolumab Injection ^a	10 mg/mL; 100-mg fill volume and 10 mg/mL; 40-mg fill volume	IP	Open Label	Vials	Refer to the label or container and/or Pharmacy Manual
Abemaciclib Tablets ^b	150 mg, 100 mg, and 50 mg	IP	Open Label	Tablets	Refer to the label or container and/or Pharmacy Manual
Palbociclib Capsules ^b	125 mg, 100 mg, and 75 mg	IP	Open Label	Capsules	Refer to the label or container and/or Pharmacy Manual
Anastrozole Tablets ^b	1 mg	IP	Open Label	Tablets	Refer to the label or container and/or Pharmacy Manual

Abbreviations: IP = investigational product; IMP, investigational medicinal product; mg = milligram; mL = milliliter; SmPC = summary of product characteristics.

^a May be labeled as either “BMS-936558-01” or “Nivolumab”.

^b These products may be obtained by the investigational sites as local commercial product in certain countries if allowed by local regulations. In these cases, products may be a different pack size/potency than listed in the table. These products should be prepared/stored/administered in accordance with the package insert or SmPC or according to institutional standards.

7.1 Treatments Administered

The selection and timing of dose for each participant are shown in Table 7.1-1 and Table 7.1-2.

Table 7.1-1: Selection and Timing of Dose - Safety Run-in Phase

Cohort	Study Treatment	Dosage Level ^a	Frequency of Administration	Start and Duration of Treatment	Route of Administration
1	Nivolumab	480 mg	Q4W	Cycle 1-5	IV
	Abemaciclib	150 mg	BID	Cycle 1-5	PO (with or without food)
	Anastrozole	1 mg	QD	Cycle 1-5 ^b	PO (with or without food)
2	Nivolumab	480 mg	Q4W	Cycle 1-5	IV
	Palbociclib	125 mg	QD × 3 weeks on (1 week off)	Cycle 1-5	PO (with food)
	Anastrozole	1 mg	QD	Cycle 1-5 ^b	PO (with or without food)

Abbreviations: BID = twice daily; EOT = end of treatment; IV = intravenous; mg = milligram; PO = per os (by mouth); Q4W = every 4 weeks; QD = once daily.

Note: At the time of Revised Protocol 03, 2 participants had been treated in Cohort 1 (nivolumab + abemaciclib + anastrozole), which was subsequently closed for enrollment.

^a For abemaciclib and palbociclib, this is the starting dose level. Dose levels may be reduced per [Section 7.4](#) (Dosage Modification).

^b After 5 cycles or EOT, all participants should continue to receive anastrozole until breast surgery. Anastrozole is not considered study therapy beyond completion of Cycle 5 or EOT.

Table 7.1-2: Selection and Timing of Dose - Randomized Phase

Arm	Study Treatment	Dosage Level ^a	Frequency of Administration	Start and Duration of Treatment	Route of Administration
A	Nivolumab	480 mg	Q4W	Cycle 1-5	IV
	Palbociclib	125 mg	QD × 3 weeks on (1 week off)	Cycle 1-5	PO (with food)
	Anastrozole	1 mg	QD	Cycle 1-5 ^b	PO (with or without food)
B	Palbociclib	125 mg	QD × 3 weeks on (1 week off)	Cycle 1-5	PO (with food)
	Anastrozole	1 mg	QD	Cycle 1-5 ^b	PO (with or without food)
	Nivolumab	480 mg	Q4W	Cycle 2-5	IV

Table 7.1-2: Selection and Timing of Dose - Randomized Phase

Arm	Study Treatment	Dosage Level ^a	Frequency of Administration	Start and Duration of Treatment	Route of Administration
C	Palbociclib	125 mg	QD × 3 weeks on (1 week off)	Cycle 1-5	PO (with food)
	Anastrozole	1 mg	QD	Cycle 1-5 ^b	PO (with or without food)

Abbreviations: BID = twice daily; EOT = end of treatment; IV = intravenous; mg = milligram; PO = per os (by mouth); Q4W = every 4 weeks; QD = once daily.

Note: As of Revised Protocol 03, the abemaciclib-containing combination arms have been removed from the Randomization Phase of the study.

^a For palbociclib, the starting dose level will be the safe dose determined upon completion of the Safety Run-in Phase.

^b After 5 cycles or EOT, all participants should continue to receive anastrozole until breast surgery. Anastrozole is not considered study therapy beyond completion of Cycle 5 or EOT.

Randomized participants should begin study treatment within 3 calendar days of randomization.

7.1.1 Nivolumab Dosing (Safety Run-in Cohorts and Randomized Phase Arms A and B)

Participants are to start nivolumab within 3 calendar days of randomization. Participants will receive nivolumab at a dose of 480 mg as a 30-minute IV infusion for a maximum of 5 cycles (maximum 4 cycles for Arm B).

Doses of nivolumab may be interrupted, omitted, or discontinued, depending on how well the participant tolerates the treatment. There will be no dose escalations or reductions of nivolumab allowed. For Q4W dosing cycles, participants may be dosed within a \pm 3-day window.

If a participant cannot receive nivolumab within a \pm 3-day window, nivolumab must be omitted (skipped) for that cycle. If nivolumab is omitted, the other study medications may continue. If a participant discontinues nivolumab, the entire study treatment (CDK4/6 inhibitor and anastrozole) must be discontinued.

When nivolumab is scheduled to be administered on the same day with palbociclib plus anastrozole, nivolumab dosing should be started > 1 hour after palbociclib plus anastrozole ingestion. If nivolumab can not be given within 3 days of palbociclib plus anastrozole administration for a given cycle, nivolumab must be omitted for that cycle.

Premedications are not recommended for the first dose of nivolumab.

Participants should be carefully monitored for infusion reactions during nivolumab administration. If an acute infusion reaction is noted, participants should be managed according to [Section 7.4.4.3](#) (Treatment of Nivolumab Infusion Reaction).

Instructions for dilution and infusion of nivolumab injection may be provided in the clinical protocol, pharmacy binder, or pharmacy reference sheet. Care must be taken to assure sterility of

the prepared solution, as the product does not contain any antimicrobial preservative or bacteriostatic agent.

7.1.2 CDK4/6 Inhibitors and Anastrozole Dosing

Premedications are not recommended for the first dose.

In the Safety Run-in Phase, participant assignment to abemaciclib or palbociclib will be carefully managed by the study team with the Investigator. The selected CDK4/6 inhibitor cannot be changed or switched to another one once the study treatment has been initiated. At implementation of Revised Protocol 03, the study will only evaluate the combination of nivolumab with palbociclib plus anastrozole. Patients in screening and not yet treated were offered the option to join the nivolumab + palbociclib + anastrozole arm. Patients on treatment were to be re-consented and continue on anastrozole alone, OR taken off study.

Study treatment must be taken within 3 calendar days following randomization.

In the Randomized Phase, participants will be randomly assigned by an IRT system.

Palbociclib should be taken together with anastrozole as follows:

- Palbociclib is dosed QD PO for the first 3 weeks of the cycle (with the 4th week off). Anastrozole is dosed continuously, BID and QD PO, respectively.
- On scheduled visit days, participants must hold taking study treatments at home. They must take them in the clinic under the supervision of the Investigator or designee after all study procedures for the visit have been completed. On all other days, participants may take study treatments at home.
- Participants should be instructed to take palbociclib and anastrozole with a large glass of water (~250 mL or ~8 oz) at the same time each day.
- Palbociclib should be administered with food. Anastrozole can be administered either with or without food.
- Participants should be instructed to swallow the tablets whole and not to chew, crush, or open them.
- If vomiting occurs during the course of treatment, no re-dosing of the participant is allowed before the next scheduled dose. The occurrence and frequency of any vomiting during a treatment cycle must be noted in the AEs section of the eCRF.
- Any doses that are missed (not taken within 6 hours of the intended time) should be skipped and should not be replaced or made up on a subsequent day.
- Multivitamins, glucosamine, probiotics, and fish oil are permitted.
- After 5 cycles or EOT, all participants should continue to receive anastrozole until subsequent breast surgery. If anastrozole can no longer be administered after EOT (ie, due to related toxicities), breast surgery will be performed right away. Anastrozole is not considered study therapy beyond completion of Cycle 5 or EOT.

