Dispense Anastrozole 1 mg and Provide and Review Patient Diary (Safety Run-in Cohorts and all Arms)	X					To be administered QD PO, with or without food. Review patient diary at each study visit. Note: Anastrozole given beyond C5 or beyond EOT will not be considered as study treatment and must be collected as concomitant medication.
AND						
Dispense Abemaciclib and Provide/Review Patient Diary (Safety Run-in Cohort 1) ^e	X					To be administered BID PO with or without food. Review patient diary at each study visit.
OR						
Dispense Palbociclib and Provide/Review Patient Diary (Safety Run-in Cohort 2 and Arms A, B, and C)	X					To be administered QD PO with food during the first 3 weeks of each cycle (1 week off). Review patient diary at each study visit.

Abbreviations: AE = adverse event; BC = breast cancer; BCS = breast-conserving surgery; BID = twice daily; BP = blood pressure; C = cycle; CBC = complete blood count; D = day; ECG = electrocardiogram; ECOG = Eastern Cooperative Oncology Group; eCRF = electronic case report form; EOT = end of treatment; HR = heart rate; IRT = interactive response technology; IV = intravenous; mg = milligram; PE = physical examination; PO = per os, (by mouth); PS = performance status; QD = daily; Q4W = every 4 weeks; SAE = serious adverse event.

[figure not shown]
- a The schedule for each procedure should coincide with actual dosing.
 - b Participants will undergo surgical treatment within 4 weeks of the last dose of neoadjuvant treatment (IV or oral, whichever comes later).
 - c On-treatment procedures may generally be performed within a ± 3 -day window, unless otherwise specified (eg, breast ultrasound or mammogram, tumor biopsy).
 - d Some of the assessments referred to in this section may not be captured as data in the eCRF. They are intended to be used as safety monitoring by the treating physician. Additional testing or assessments may be performed as clinically necessary or where required by institutional or local regulations.
- 

Table 2-3: Follow-up Procedural Outline (Safety Run-in Phase and Randomized Phase; CA2097A8)

Procedure	30-Day Safety Follow Up (FU1) ^a (± 7 days) (All Participants in the Safety Run-in Phase and the Randomized Phase)	100-Day Safety Follow Up (FU2) ^a (± 7 days) (All Participants in the Safety Run-in Phase and Arms A and B Only in the Randomized Phase)	Notes ^b
Safety Assessments			

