5.1.2.1 Safety Run-in Phase

As of Revised Protocol 03, Cohort 1 will be discontinued. Participants in screening and not yet treated were offered the option to join the nivolumab + palbociclib + anastrozole arm. Participants on treatment were to be re-consented and continue on anastrozole alone, OR taken off study.

The Safety Run-in Phase will be conducted in advance of the Randomized Phase to evaluate the safety and tolerability of the combination of nivolumab, with palbociclib, plus anastrozole, which will be administered during the Randomized Phase.

Participants will receive palbociclib in combination with nivolumab plus anastrozole (Cohort 2) for 5 cycles as neoadjuvant therapy and be followed up for safety (see [Section 5.1.3](#) [Safety Follow-up Period]). For the purpose of guiding alternative dose levels, all AEs will be graded according to the National Cancer Institute (NCI) Common Terminology Criteria for Adverse Events (CTCAE) v5.0 and dose-limiting toxicities (DLTs) will be defined based on the incidence, intensity, and duration of the AEs for which no clear alternative cause is identified. For the purpose of participant management, any drug-related AE that meets DLT criteria will lead to discontinuation of study treatment.

Participants who have discontinued due to a DLT or who have received 1 dose of nivolumab and 75% of accumulative doses of palbociclib of the cycle, and have completed the 4-week DLT period will be considered as DLT-evaluable participants. Participants who withdraw from the study during the DLT evaluation period or have received less than 1 dose of nivolumab and 75% of accumulative doses of palbociclib of the cycle for reasons other than a DLT will not be considered as DLT-evaluable participants and may be replaced with new participants at the same dose level.

[figure not shown]
Dose De-escalation Rules

For Cohort 2, 3 DLT-evaluable participants will be treated with the below starting doses:

- Nivolumab: 480 mg every 4 weeks (Q4W) intravenously (IV)
- Palbociclib 125 mg once daily (QD) PO for 3 weeks of each cycle (1 week off)
- Anastrozole: 1 mg QD PO

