 - a) palbociclib 125 mg QD PO for 3 weeks of each cycle (1 week off) + anastrozole 1 mg QD PO for 1 cycle followed by
 - b) nivolumab 480 mg Q4W IV + palbociclib 125 mg QD PO for 3 weeks (1 week off) + anastrozole 1 mg QD PO for 4 cycles
- 3) Arm C (control palbociclib arm): palbociclib 125 mg QD PO for 3 weeks of each cycle (1 week off) + anastrozole 1 mg QD PO for 5 cycles

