5.6.2 Justification for Dose of CDK4/6 Inhibitors

Abemaciclib 150 mg BID PO or palbociclib 125 mg QD PO for 3 weeks of each cycle (1 week off) were approved by FDA in Sep-2017 and Feb-2015, respectively, and by EMA in Sep-2018 and Nov-2016, respectively, in combination with ET for ER+, HER2- BC, based on clinical safety and efficacy.

Abemaciclib 150 mg BID PO or palbociclib 125 mg QD PO for 3 weeks of each cycle (1 week off) will be examined in combination with nivolumab and anastrozole in this study.

As of Revised Protocol 03, examination of abemaciclib + nivolumab + anastrozole will not be continued in this study.

5.6.3 **Justification for Dose of Anastrozole**

Anastrozole 1 mg QD PO was approved by FDA and in Europe in Jan-1996 and Aug-1995, respectively, for BC.

Anastrozole 1 mg QD PO will be examined in combination with nivolumab and palbociclib in this study.

6 **STUDY POPULATION**

For entry into the study, the following criteria **MUST** be met.

6.1 **Inclusion Criteria**

1) **Signed Written Informed Consent**

- a) Participants must have signed and dated an Institutional Review Board (IRB)/Independent Ethics Committee (IEC)-approved written ICF in accordance with regulatory and institutional guidelines. This must be obtained before the performance of any protocol-related procedures that are not part of normal patient care.
- b) Participants must be willing and able to comply with scheduled visits, treatment schedule, laboratory tests, tumor biopsies, and other requirements of the study.

2) **Type of Participant and Target Disease Characteristics**

- a) Participants must have histologically confirmed unilateral invasive breast carcinoma, with the following characteristics:
 - i) Primary tumor ≥ 2 cm in largest diameter (cT1-3) by US/mammogram. In the case of a multifocal tumor (defined as the presence of two or more foci of cancer within the same breast quadrant), the largest lesion must be ≥ 2 cm and designated as the “target” lesion for all subsequent tumor evaluations. Please note: N3 disease (defined so either clinically or radiologically) is excluded.
 - ii) In participants where there may be a reasonable suspicion of advanced disease (eg, large tumors, clinically positive axillary lymph nodes, signs and symptoms), documentation confirming the absence of distant metastasis (M0) as determined by institutional practice is required (staging imaging reports).
 - iii) *Not applicable per Revised Protocol 03.*

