9.3 Overdose

An overdose is defined as the accidental or intentional administration of any dose of a product that is considered both excessive and medically important. Overdoses that meet the regulatory definition of SAE will be reported as an SAE (refer to [Appendix 3](#)).

All instances of accidental overdose and/or dosing errors should be reported on the Dosage Administration Record eCRF.

For this study, any dose of nivolumab, abemaciclib, palbociclib, or anastrozole that is greater than the scheduled dose within a 24-hour time period will be considered an overdose.

In the event of an overdose the Investigator should:

- 1) Contact the Medical Monitor immediately.
- 2) Closely monitor the participant for AEs/SAEs and laboratory abnormalities until study treatment can no longer be detected systemically (at least 5 days for abemaciclib or palbociclib, and at least 10 days for anastrozole).
- 3) Document the quantity of the excess dose as well as the duration of the overdosing in the eCRF.

Decisions regarding dose interruptions or modifications will be made by the Investigator in consultation with the Medical Monitor based on the clinical evaluation of the participant.

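### Protocol Section 7.1.2 gives anastrozole two dosing frequencies in one sentence, at odds with the single frequency stated everywhere else in the protocol and SAP

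*Protocol*

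**What the plan says.** Section 7.1.2 of the protocol introduces a list of instructions for taking palbociclib together with anastrozole. Its first bullet gives palbociclib once daily for three weeks of each cycle and then, in a separate sentence, states: "Anastrozole is dosed continuously, BID and QD PO, respectively". A later bullet in the same list fixes a common daily time for the two drugs: "Participants should be instructed to take palbociclib and anastrozole with a large glass of water (~250 mL or ~8 oz) at the same time each" (quote cut before its last word).

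Elsewhere the protocol gives one frequency:

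- Table 2-2 (Schedule of Activities), the row on dispensing anastrozole and the patient diary: "To be administered QD PO, with or without food. Review patient diary at each study visit".
- Section 5.1.2.1, run-in starting doses: "Anastrozole: 1 mg QD PO".
- Section 5.1.2.2, arm definitions, here Arm C: "palbociclib 125 mg QD PO for 3 weeks of each cycle (1 week off) + anastrozole 1 mg QD PO for 5 cycles". Arms A and B carry the same anastrozole frequency.
- Section 5.6.3, dose justification: "Anastrozole 1 mg QD PO will be examined in combination with nivolumab and palbociclib in this study".
- Tables 7.1-1 and 7.1-2, every anastrozole row: "Anastrozole 1 mg QD Cycle 1-5 ^b PO (with or without food". The synopsis tables repeat these rows.

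The SAP agrees with this group: Section 2.2 (both phases), the run-in regimens in Section 6.2, and Table 7.4.1-2, which lists the protocol schedule as 1 mg QD with a planned average daily dose of 1 mg.

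Section 9.3 covers any dose of a study drug, anastrozole included, "that is greater than the scheduled dose within a 24-hour time period will be considered an overdose". It gives no milligram threshold.

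**The concern.** The sentence cannot be followed as written. The word respectively calls for two subjects; there is only one, because palbociclib's frequency has already been given in the sentence before. A reader is left to choose between the two frequencies or to look elsewhere.

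Anastrozole is given in all three randomized arms and in the run-in cohorts, participants may take it at home on days without a scheduled visit, and Section 7.1.2 is where a site would look for how to instruct them. Section 9.3 also depends on there being one defined schedule, since it measures an overdose against that schedule and then requires immediate contact with the Medical Monitor and at least 10 days of monitoring for anastrozole. With two frequencies in the text, the threshold for that rule is unclear.

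**Working it through.** **Step 1. Is the sentence live text?** Yes. It stands in the body of Revised Protocol 03, not in the summary of changes, and no redaction falls within it.

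**Step 2. Side-by-side comparison of anastrozole frequency.**

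| Place | Frequency |
|---|---|
| Protocol 7.1.2 | BID and QD, one drug named |
| Protocol synopsis tables | QD |
| Protocol Table 2-2 | QD |
| Protocol 5.1.2.1 | QD |
| Protocol 5.1.2.2, Arms A to C | QD |
| Protocol 5.6.3 | QD |
| Protocol Tables 7.1-1 and 7.1-2 | QD |
| SAP 2.2, run-in and randomized phases | QD |
| SAP 6.2, run-in regimens | QD |
| SAP Table 7.4.1-2 | QD |

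Section 7.1.2 is the only place that differs. It also sits uneasily with itself, since the later bullet on taking the two drugs at the same time each day implies one intake a day.

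**Step 3. Where the second frequency may come from.** The only drug scheduled BID in the documents is abemaciclib, 150 mg in run-in Cohort 1 (Table 7.1-1). Sections 7.4.1 and 8.1.2 say its dosing stops in all patients when Revised Protocol 03 is implemented. A sentence that once named abemaciclib and anastrozole would fit BID and QD in that order. This is inference; the documents do not say so.

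**Step 4. Reproduce the SAP's planned daily doses (Table 7.4.1-2).**

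- Anastrozole: 1 mg × 1 per day = 1 mg/day, as stated.
- Abemaciclib: 150 mg × 2 = 300 mg/day, as stated.
- Palbociclib: 125 mg × 21/28 = 93.75 mg/day, as stated.

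The SAP's planned anastrozole dose therefore rests on QD.

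**Step 5. What the two readings would give.** Relative dose intensity = actual average daily dose / planned average daily dose × 100. Section 7.1.2 states no strength, so the 1 mg must be borrowed from the tables. Five cycles of 28 days are 5 × 28 = 140 days.

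| Reading | mg per 24 h | mg over 140 days | Relative dose intensity |
|---|---|---|---|
| QD | 1 | 140 | 1/1 × 100 = 100% |
| BID | 2 | 280 | 2/1 × 100 = 200% |

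The BID result falls in the SAP's highest category, 110% or more (Section 7.4.1).

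**Step 6. The overdose rule.** If the scheduled dose is the tabulated 1 mg QD, 2 mg in 24 hours exceeds it. If Section 7.1.2 is taken as part of the schedule, it is unclear what 2 mg should be compared with. The rule itself is not contradicted; its reference point becomes ambiguous.

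**The case against.** The strongest reply is that this is a copy-editing remnant and that the rest of the documents neutralise it. Section 7.1 points the reader to Tables 7.1-1 and 7.1-2 for the selection and timing of dose, and both give one frequency. So does Table 2-2, in the row that covers dispensing and the diary. Section 7.1.2 has palbociclib and anastrozole taken together. A site that noticed the stray frequency would have many consistent statements with which to resolve it. All of this stands and lowers the practical risk. It does not remove a faulty frequency from the section that instructs sites on oral dosing.

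Three stronger readings are tempting and are not supported:

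- *That the sentence contradicts the overdose rule.* Section 9.3 names no milligram figure. Twice-daily intake is an overdose only once the 1 mg QD schedule has been assumed, which presupposes that the conflict is settled.
- *That it distorts the exposure analysis.* No SAP definition uses the BID wording. Had a participant taken 2 mg/day, the SAP's formula would report 200% and place it in the top category, which is a correct description of a departure from plan.
- *That it affects all of the approximately 115 to 136 participants.* Anastrozole is planned for all of them, but nothing shows that any site read the sentence as BID, and the wording of the patient diary is not in the documents.

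**Conclusion.** The inconsistency is certain: one drug, two frequencies, in current dosing text, against a single frequency in every other place listed above. It is an internal inconsistency and should not be read as a design choice. Its practical weight is small, because the surrounding text is consistent, but the subject is how participants take a study drug at home, so it is worth correcting.

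The size, 2 mg/day against a planned 1 mg/day (200%), rests on two assumptions: that someone followed the BID wording, and that they used the 1 mg strength from the tables. It describes a possible consequence and is not an estimate of what occurred. The leftover-text explanation is likely but unproven. Sample size, power, endpoints and analysis populations do not depend on this point. No view is taken here on which frequency is correct.

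**What to change.** The sponsor should reconcile the anastrozole sentence in Section 7.1.2 with Table 2-2, Sections 5.1.2.1, 5.1.2.2 and 5.6.3, Tables 7.1-1 and 7.1-2, the synopsis tables, and SAP Sections 2.2 and 6.2 and Table 7.4.1-2, so that one frequency is stated throughout. Once that is done, the scheduled dose in Section 9.3 has a single meaning and needs no rewording of its own. The cost is one sentence in the protocol; the statistical design is unchanged.
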